body weight per day, and who are unlikely to tolerate substantial enteral nutrition until several months following their small intestinal insult.

II. Purpose of Study

The specific aim of this study is to ascertain whether PNAC can be reversed if a fish oil-based intravenous lipid product (Omegaven®) at a dose of up to 1 g/kg body weight/day is substituted for a soy-based intravenous lipid product (Liposyn® or Intralipid®) as part of the daily TPN of infants and children with intestinal failure and PNAC. Secondary aims will be to confirm the safety of Omegaven®.

III. Background

In North America, infants and children who require parenteral nutrition (TPN) customarily receive solutions whose caloric distribution is balanced between glucose, protein, and fat to provide approximately 60-70 % of calories via glucose, 10-15 % of calories via protein, and 20-30% of calories via lipid.(1) Commercial lipid solutions utilized in North America are customarily soy-based, and contain high quantities of phytosterols including sitosterol and stigmasterol. Animal data suggest that high quantities of stigmasterol inhibit fxr, a nuclear receptor in the hepatocyte that helps to regulate bile acid homeostasis by controlling expression of bile acid export pumps. (2) Thus, exposure to a high quantity of stigmasterol is potentially hepatotoxic to individuals who have a propensity for cholestasis due to a poorly developed bile secretory process.

It is known that infants and children with underlying intestinal failure are at extraordinarily high risk for cholestasis. (3) The cholestatic process is reversible in approximately ¼ of infants with parenteral nutrition associated cholestasis (PNAC), even when soy-based lipid emulsions are given parenterally, if those infants can experience small intestinal adaptation and ultimately tolerate and assimilate the majority of their calories via enteral nutrition. Unfortunately, if adaptation does not occur rapidly enough, PNAC may progress to endstage liver disease resulting in death or necessitating combined liver/small intestinal transplantation.

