PNAC is a potentially fatal disorder, and the consequences are heinous if the process cannot be reversed. In Omegaven® we have an agent that is potentially life saving, and its use in hundreds of patients has shown little if any toxicity. After ongoing controlled trials of Omegaven® are completed, the agent will be evaluated for approval by the FDA. Until such time as FDA approval is granted, we will be unable to administer Omegaven® without requesting approval for compassionate use. The IRB granted approval for protocol 2009-1041, and this protocol will call for even stricter inclusion criteria. Therefore, we seek IRB approval for this study.

IV. Duration of Study

Once IRB approved, enrollment of subjects into this study will occur for up to 9 years. Subjects will receive Omegaven at a dose of up to 1 g/kg body weight/day until they no

longer require TPN or until their conjugated or direct bilirubin has normalized and their enteral lipid intake is sufficient to discontinue intravenous lipids.

A total study duration of 10 years is anticipated to complete the study (enrollment, analyses, and report writing).

V. Potential Benefits

The use of Omegaven® has the potential to benefit patients with PNAC by facilitating the resolution of cholestasis.

VI. Potential Risks of Omegaven® Treatment

Omegaven® has been studied in animal pre-clinical models as well as Phase I, II, III, and post marketing human trials in both Europe and Asia. Prolonged bleeding time and an inhibited platelet aggregation can occur. It should not be administered to patients known to be allergic to fish or egg protein.

Contraindications to Omegaven® include the following:

1. Impaired lipid metabolism
2. Severe hemorrhagic disorders
3. Unstable diabetes mellitus
4. Collapse and shock
5. Stroke/Embolism
6. Recent cardiac infarction
7. Undefined coma status

Side Effects:

Risks of Omegaven®

The infusion of Omegaven® can lead to a prolonged bleeding time and an inhibited platelet aggregation. In rare cases, patients may experience a fishy taste.

The administration of Omegaven® should be stopped or reduced if there is a marked increased in blood glucose levels during the Omegaven® infusion. Undesirable effects that are seen during the infusion of Omegaven® that may also occur with conventional fat emulsions (i.e., Liposyn® or Intralipid®) include:

1. Slight rise in body temperature
2. Heat sensation and/or cold sensation
3. Chills
4. Flushing or cyanosis

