 - Impaired lipid metabolism (triglycerides >1000 mg/dL) while on 1g/kg/day or less of Intralipid
 - History of severe hemorrhagic disorders (ie. hemophilia, Von Willebrand disease, etc.)
 - Unstable diabetes mellitus
 - Collapse and shock
 - Stroke/Embolism
 - Cardiac infarction within the last 3 months
 - Undefined coma status
 - Pregnancy (positive pregnancy test) prior to enrollment in the study for females of child-bearing potential
 - Females of child-bearing potential who are unwilling to use birth control during study participation
2. Parental decision to forego the use of Omegaven®
3. Known fish or egg allergy
4. Pregnancy
5. Causes of liver disease other than PNAC

B. Withdrawal Criteria

1. Decision of an assenting minor/adult subject or parent/guardian to withdraw from the study*
2. Anaphylaxis
3. Evidence of spur cell anemia.
4. Increasing anemia (hemoglobin < 7 g/dL) in the absence of gastrointestinal bleeding.
5. Mucosal bleeding or bleeding from IV insertion sites requiring transfusion.
6. Reproducible priapism associated temporally with the infusion
7. Mucosal bleeding associated with abnormal platelet function
8. Bowel adaptation such that patient can either come off TPN or such that enteral fat can meet the patient's nutritional requirements
9. Patient undergoes liver transplantation
10. Pregnancy
11. Patient is lost to follow up

* If an assenting minor chooses to withdraw from the study early, even if the parent wants the child to participate, the child will have their wishes respected.

C. Stopping Rules

If two subjects develop the same grade-3 adverse event (including liver function tests, Protocol – Compassionate Use of a Fish Oil-derived Intravenous Fat Emulsion (Omegaven®) to Reverse Parenteral Nutrition (PN) Induced Cholestasis

coagulation profile, and platelet count) related to the study medication that is irreversible upon de-escalation (does not reverse after 10 days) or upon discontinuation of the study drug, or any subject develops a related grade-4 adverse event, these events will be the cause for termination of the study.

D. Monitoring for toxicity due to Omegaven®

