For those determined to be eligible, the following will occur:

- Complete medical history and physical exam
- Baseline Blood Tests including:
 - TPN panel
 - Liver profile
 - Renal profile

- Ca
- P04
- Mg
- Triglycerides
 - Essential fatty acid levels
 - Thromboelastography (TEG) - with platelet mapping preferred
 - CBC, differential, platelets.
 - PT/PTT (at outset and then monthly)
 - Cholesterol
- Pregnancy test (urine) for females of child-bearing potential.

All patients will be followed as inpatients within the Regional Center for Neonatal Care (RCNC), the Department of Surgery, and the Division of Gastroenterology. As outpatients they will be followed within the Comprehensive Nutrition Clinic (CNC). Laboratory monitoring of patients with intestinal failure on TPN can be found on Compliance 360. Inpatients undergo the same monitoring, but a TPN panel and CBC are performed once weekly. Outpatients will undergo weekly monitoring of vital signs and fluid balance as well as inspection of gastrostomies, enterostomies, and central venous catheter exit sites by home healthcare nurses.

While they are on Omegaven® they will be seen and examined twice a month for study visits, and they will undergo blood sampling twice a month to obtain repeat levels of their baseline tests for the first 6 months. After the first 6 months, they will be seen and examined monthly and will undergo monthly blood sampling. Adverse events and concomitant medication information will be collected and documented at each study visit.

Below is a description of the study procedures:

Medical History and Physical

A complete, comprehensive history and physical will be performed at the beginning and end of the study. An interim medical history and a brief physical exam will be performed at all other study visits.

Clinical and demographic data will also be obtained to include: age, gender, race, and current medications.

At other study visits, an abbreviated physical exam will be performed and changes in medical history or concomitant medications will be noted.

Phone Calls:

For the first 6 months of the study, a study coordinator will contact research participants/families weekly to assess for any changes in health status and changes to medications. Thereafter, the coordinator will contact participants/ families monthly

approximately midway between monthly clinic visits. Changes in clinical status and concomitant medications will be monitored until the end of the study.

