Following completion of the study medication, subjects will be seen for a final study visit within 1 month for a follow-up assessment. A complete, comprehensive history and physical will be performed. Blood samples will be collected and a urine pregnancy test will be done for females of childbearing potential. Adverse events and concomitant medications will be documented by the study staff.

The following table summarizes Study Procedures:

Study Procedures Table

	Baseline (Day 0)	Weekly while Inpatient	Weekly for first 6 months	Twice a month for the first 6 months	Monthly	Final Visit (within 1 month after treatment)
Signed informed consent/assent	X					
History	X			X	X	X
Physical Exam	X	X		X	X	X
Blood specimen (4.4 mcl using microtainers) [#]	X	X		X	X	X
Urine pregnancy test*	X				X	X
Phone calls (clinical status and concomitant medication collection)			X		X **	

At baseline and then monthly for PT/PTT. At baseline and then weekly for other laboratory studies (see Section IX, E).

* For females of child-bearing potential.

** Phone calls will take place monthly (between the monthly visits)

G. Data Collection

Demographic and clinical information will be collected whenever clinical data are available via uniform baseline and follow up clinical data extraction forms to ensure accuracy and consistency. The essential demographic information includes age at diagnosis, gender, race and ethnicity, birth history, past medical history, and family history. The clinical information includes presence or absence of jaundice, hepatosplenomegaly, or ascites.

H. Compensation

Participants will not be compensated for study participation. Subjects will receive study medication, clinical supplies, and laboratory evaluations that are obtained outside the standard of care free of charge.

I. Withdrawal

Protocol – Compassionate Use of a Fish Oil-derived Intravenous Fat Emulsion (Omegaven[®]) to Reverse Parenteral Nutrition (PN) Induced Cholestasis

Data collected from patients who withdraw from the study will be included in the final analysis using intent to treat. Patient enrollment will continue until all 25 patients complete all requested study requirements outlined. It will be recommended that patients withdrawn from the protocol resume a reduced lipid intake, treat infections promptly as they occur and advance feedings as quickly as tolerated.

X. Assessment of Efficacy

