The primary endpoint will be reduction in conjugated or direct bilirubin level to below 1 mg/dl. Data from previous retrospective analyses and prospective uncontrolled studies suggest that from the inception of Omegaven® therapy, conjugated or direct bilirubin will remain elevated for approximately 8 weeks at levels comparable to those observed prior to administration of Omegaven®. Subsequently, levels are expected to fall by approximately 1 mg/dl/week until they normalize. The time to normalization will vary according to each patient's baseline conjugated or direct bilirubin level. Thus, a patient who begins Omegaven® with a conjugated or direct bilirubin level of 7 mg/dl is likely to experience normalization within 14 weeks (8+6 weeks). We will compare the group receiving Omegaven® with historical controls from our internal registry who have demonstrated cholestasis while on Intralipid®. We will compare changes in conjugated/direct bilirubin concentration over time between groups via Kaplan-Meier analysis (see Statistics section XIII).

Secondary endpoints will be: normalization of total bilirubin and liver enzymes. Differences in these values at the end of 14 weeks of therapy will be compared with those of controls via Kaplan-Meier analysis identical to that employed for conjugated and direct bilirubin levels. Furthermore, we expect that elevated triglyceride levels which might be present at the initiation of therapy will have normalized at the same time that liver profiles have normalized.

XI. Assessment of Safety/Data Safety Monitoring Board

A DSMB will monitor the study for the occurrence of adverse events (both serious and otherwise). A significant increase in the rate of adverse events would be cause for concern for the safety of participants in the study. Information on adverse events will be presented in several ways: (1) listings of serious adverse events with accompanying narrative summary by the PI; (2) summaries of adverse events by body system and type of event. This information will be presented to the DSMB.

The DSMB will also monitor the efficacy and the conduct of the study. Interim monitoring reports for the DSMB will include, but will not be limited to, such tabulations as:

1. platelet counts
2. essential fatty acid profiles
3. coagulation studies
4. liver profiles

5. renal profiles

The DSMB will meet at least once per year and possibly more frequently given the expected speed of recruitment and study medication administration.

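### Children who adapt early can leave the study before the bilirubin endpoint is due, and no later bilirubin is scheduled, so the outcome is lost at a prognosis-related exit

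*Combined protocol and SAP*

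**What the plan says.** - **Exit.** Section IX.B, item 8, lists as a withdrawal criterion: "Bowel adaptation such that patient can either come off TPN or such that enteral fat can meet the patient's nutritional requirements". It sets no bilirubin condition.
- **Treatment duration.** Section IV continues Omegaven until subjects no "longer require TPN or until their conjugated or direct bilirubin has normalized and their enteral lipid intake is sufficient to discontinue intravenous lipids". On the enteral-fat route this does require normalized bilirubin, which item 8 does not.
- **Measurement.** Section IX.F ties visits and bloods to treatment: "While they are on Omegaven® they will be seen and examined twice a month for study visits", becoming monthly after 6 months. Then: "Following completion of the study medication, subjects will be seen for a final study visit within 1 month for a follow-up assessment". That visit includes a blood draw ("Blood samples will be collected and a urine pregnancy test will be done for females of childbearing potential"). No later bilirubin is scheduled.
- **Endpoint and expected course.** Section X sets the primary endpoint as conjugated or direct bilirubin below 1 mg/dl. It expects that "conjugated or direct bilirubin will remain elevated for approximately 8 weeks at levels comparable to those observed prior to administration" of Omegaven, followed by a fall of about 1 mg/dl per week. The secondary comparison is placed at 14 weeks of therapy.
- **Prognosis.** Section III says cholestasis reverses in about a quarter of infants even on soy lipid "if those infants can experience small intestinal adaptation and ultimately tolerate and assimilate the majority of their calories via enteral nutrition". The opening summary before Section II adds that reversal may fail when less than about 70% of calories are enteral.
- **Analysis.** Section IX.I says: "Data collected from patients who withdraw from the study will be included in the final analysis using intent to treat". It also says enrollment runs until 25 patients complete. Sections X and XIII plan Kaplan-Meier and Cox analyses against registry controls. They give no rule for a child who exits unresolved and no follow-up horizon common to both groups.

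**The concern.** Exit under item 8 depends on a factor that the protocol regards as predictive of the outcome. A child who adapts before bilirubin has normalized leaves the schedule with the endpoint unseen, although that child's chance of resolving is, on the protocol's own account, better than average. Kaplan-Meier and Cox methods assume that censored children have the same later prospects as those still under observation, and here they would not. Counting the leavers as unresolved is no better, because some of them will resolve.

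The intent-to-treat sentence does not close the gap. It covers data that were collected, and the schedule does not require the data that matter. In a cohort of 25 a handful of such children would visibly move the primary result.

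**Working it through.** **Inputs.** From Section X: about 8 flat weeks, then about 1 mg/dl per week, endpoint below 1 mg/dl. From Section IX.A: entry bilirubin of at least 3 mg/dl. From Section IX.F: last draw 0 to 1 month after stopping, where 1 month = (365/12)/7 ≈ 4.35 weeks. Two assumptions favor the plan or simplify: the final visit takes place for withdrawn children too, and the expected course continues after Omegaven stops.

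**Step 1: expected normalization week.** T = 8 + (B − 1), with B the baseline in mg/dl. The plan's own example, B = 7, gives 8 + 6 = 14 weeks, which reproduces Section X.

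**Step 2: which stops miss the endpoint.** With the final visit as late as allowed, the endpoint is missed if the stop comes before T − 4.35.

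| Baseline (mg/dl) | T (weeks) | Always missed if stopped before week |
|---|---|---|
| 3 | 8 + 2 = 10 | 10 − 4.35 ≈ 5.7 |
| 7 | 8 + 6 = 14 | 14 − 4.35 ≈ 9.7 |
| 12 | 8 + 11 = 19 | 19 − 4.35 ≈ 14.7 |

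A child who stops between that week and T is missed only if the final visit falls before T. A child who stops at or after T is observed on treatment, to within the visit spacing.

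**Step 3: illustration of the understatement.** The documents give no early-adaptation rate, so this step is assumption. Let a be the share who adapt and leave before the event. Let 80% of them and 50% of the others truly resolve (50% is borrowed from the planning rate in Section XIII; 80% is purely illustrative).

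- All followed: 0.8a + 0.5(1 − a)
- Adapters censored: 0.5
- Adapters scored unresolved: 0.5(1 − a)

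| a | All followed | Censored (shortfall) | Scored unresolved (shortfall) |
|---|---|---|---|
| 10% | 53% | 50% (3 points) | 45% (8 points) |
| 20% | 56% | 50% (6 points) | 40% (16 points) |
| 40% | 62% | 50% (12 points) | 30% (32 points) |

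With 25 subjects, each missed resolver scored unresolved costs 1/25 = 4 points.

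**Step 4: power if leavers are scored unresolved.** The plan's 19 per group is not in dispute: a matched-design formula with zero within-pair correlation, two-sided alpha 0.05 and power 0.80 gives 18.99. For 25 against 25 (the number of controls is assumed) at 50% versus 10%, the two-sided normal approximation gives 89.5% power.

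| Share lost | Lost children resolve at the average 50% | All lost children would have resolved |
|---|---|---|
| 10% | observed 0.5 × 0.9 = 45%, power 81% | observed 50 − 10 = 40%, power 70% |
| 20% | observed 0.5 × 0.8 = 40%, power 70% | observed 50 − 20 = 30%, power 42% |

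**The case against.** **Adaptation is slow in these children.** The opening summary describes children unlikely to take substantial enteral nutrition for several months. A reader might infer that the best-prognosis children as a class leave unseen, and the documents do not support that: later adapters reach the endpoint on treatment or at the final draw. But the months are counted from the intestinal insult, not from first dose. Entry already requires more than 4 weeks at 3 mg/dl or above and a lipid reduction that failed over at least 30 days. Early adaptation on study remains plausible.

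**Clinical records may be used.** Section IX.F permits research use of clinical laboratory results, and Section IX.G collects clinical information when available. So it would be wrong to infer that an intent-to-treat analysis cannot be delivered. The permission sets no horizon and does not mention withdrawn children, so the analysis is not secured either.

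**Section XIII implies faster resolution.** It expects about 50% resolved within 8 weeks, which does not fit Section X's 8 flat weeks. On that timing, an event at week 8 is always missed only if the child stops before about week 8 − 4.35 ≈ 3.7, so fewer endpoints would be lost. This stands as a limit on the size.

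**Resolution after TPN stops partly reflects adaptation.** Censoring at that point targets a different, defensible quantity. That also stands, but the plan does not say which quantity it wants.

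**The comparison with controls.** A reader might infer that the exit rule applies to one group only and biases the comparison against Omegaven. The documents do not show this. Section XIII states both planning rates while on the respective lipid, and it does not describe how controls are followed after adaptation.

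**Conclusion.** The point holds for early adapters. On Section X's expected course, a child with a baseline of 3, 7 or 12 mg/dl who stops before about week 6, 10 or 15 (later if the final visit is earlier) has no scheduled bilirubin when the endpoint would occur. Because exit is related to prognosis, either censoring these children or scoring them as unresolved can understate resolution within the Omegaven group.

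The size is unknown. The 3 to 12 points (censored) and 8 to 32 points (scored unresolved) rest on an assumed 10% to 40% share of early adapters and assumed resolution rates of 80% and 50%. Since Section X assigns Kaplan-Meier to the primary endpoint, the censoring figures are the nearer guide. The within-group error runs against Omegaven, so on its own it would not create a false claim of benefit. The net bias against controls is undetermined.

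The gap is more than missing detail: as written, the schedule stops collecting the primary endpoint at an exit that depends on prognosis. Separately, Section IV and item 8 of Section IX.B differ on whether bilirubin must have normalized on the enteral-fat route.

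**What to change.** 1. Separate end of study drug from end of data collection. For every dosed subject who has not withdrawn consent, extract conjugated or direct bilirubin, total bilirubin, liver enzymes and TPN/enteral status from routine clinical records. Continue to one fixed horizon from first dose, whether or not Omegaven continues. The sponsor should choose a horizon that covers the expected normalization time; 26 weeks is one example.
2. Apply the same horizon and the same handling of exits to the registry controls.
3. Define the secondary comparison as 14 weeks from first dose.
4. Add a sensitivity analysis that censors both groups at coming off TPN.
5. Reconcile Section IV with item 8 of Section IX.B. Which rule applies is for the sponsor to decide; the data-collection change works under either.

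The cost is a protocol amendment and chart extraction, with no study visits or blood draws added. There are two drawbacks. Results after the drug stops also reflect later lipid and feeding management, which the sensitivity analysis helps to show. Routine bilirubin tests may also be sparse once a child is off TPN, so some outcomes could still be missing.

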The DSMB chair (or designee) will be asked to review SAE reports within 7 days after initial receipt of the information by the investigator(s), to review the PIs assignment of SAEs as related or unrelated to treatment, to confirm the grading of any toxicities and assure that they do not meet stopping criteria.

A safety analysis will be performed after approximately 5 patients have received 4 weeks of treatment or, if enrollment begins slowly, 12 months after the first patient is enrolled. Safety data will be shared with the Data and Safety Monitoring Board (DSMB). There will be no further enrollment until the DSMB makes recommendations. An investigator in this study may not be a member of the DSMB. Members of the DSMB will receive safety data approximately every 2 to 3 months for review. Safety assessments will consist of vital signs, AEs, and laboratory evaluations. A cumulative listing of patient withdrawals, dose adjustments, and serious adverse events (SAEs) will also be reviewed. DSMB members will be notified of all SAEs reported expeditiously to regulatory authorities.

Study Monitoring

The Translational Research Trials Office (TRTO) will act as the independent monitor for the study. Routine monitoring visits shall occur one or more times during the period after study initiation but before study closeout. Guidelines for scheduling monitoring visits shall be determined according to the development, complexity of the study, the rate of subject accrual and other factors. Monitoring visits are conducted for routine monitoring only and are intended to ensure that the protocol and applicable regulatory requirements are being followed, that subjects' rights and safety are protected, and to confirm data integrity and quality.

XII. Adverse Events

An adverse event (AE) is any untoward medical occurrence in a patient participating in this trial. An adverse event can be an unfavorable and/or unintended sign (including an abnormal laboratory finding), symptom, syndrome or disease associated with or occurring during the use of an investigational product whether or not considered related to the investigational product.

A serious adverse event (SAE) is one that:

1. results in death
2. is life threatening
3. requires an inpatient hospitalization or prolonged a hospitalization
4. is disabling

5. is a congenital anomaly/birth defect

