As far as possible, each adverse event will be assessed by the Investigator with respect to its duration (start and end dates), the severity grade (mild, moderate, severe, life-threatening, fatal), its relationship to the drug (unrelated, unlikely to be related, possibly, probably and definitely related), the action(s) taken, the outcome (i.e. resolved, resolved with sequelae, continuing), gravity (SERIOUS or NOT SERIOUS), and expected/unexpected on the basis of drug insert.

Expected drug related events are those that have been previously identified as resulting from administration of the protocol therapy, short bowel syndrome, or parenteral nutrition as outlined in the potential risks section of this protocol or the package insert. Unexpected adverse events are those that have not been previously associated with Omegaven, short bowel syndrome, liver failure, parenteral nutrition support or any standard care for subjects with short bowel syndrome.

Adverse events will be reported by diagnosis unless a diagnosis cannot be determined.

Grading (Severity) of Adverse Events

Each adverse event will be graded to describe its intensity according to the following Severity scale:

1=	Mild:	does not interfere with patient's usual function
2=	Moderate:	interferes to some extent with patient's usual function
3=	Severe:	interferes significantly with patient's usual function

4=	Life-threatening:	puts the patient at immediate risk of death
5=	Fatal:	patient died

The NCI's Common Terminology Criteria for Adverse Events Version 4.0 (Appendix A) will be used if applicable.

Relationship to Drug

For all adverse events that occur while the patient is on drug, the relationship to the drug must be assessed by the Investigator using the following scale:

- 1 = not related
- 2 = unlikely
- 3 = possibly related
- 4 = probably related
- 5 = definitely related

For Grade > 3 adverse reactions which are possibly (3), probably (4) or definitely (5) related to the drug, study medication should be discontinued as described above.

Please note: For safety data analysis, not related and unlikely are considered "not attributable;" possible, probable and definite are considered "attributable." Assessment of relationship to drug must be carried out by the Investigator according to the 5-point scale above.

Gravity (Seriousness) of Adverse Events

Each adverse event is to be classified by the Investigator as SERIOUS or NOT SERIOUS.

Follow-Up after Adverse Events

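### The study-level stopping rule names a related grade-4 event but not grade 5, so a related event recorded only as fatal falls outside its literal wording

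*Combined protocol and SAP*

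**What the plan says.** Section IX.C (Stopping Rules) has two triggers for ending the study. The first is two subjects with the same drug-related grade-3 event that does not reverse on dose reduction or on stopping the drug. The second needs only one subject: "any subject develops a related grade-4 adverse event, these events will be the cause for termination of the study".

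Section XII sets the scale. Under Grading (Severity) of Adverse Events, "Each adverse event will be graded to describe its intensity according to the following Severity scale", and the scale that follows has five points, with 4 for life-threatening and 5 for fatal. Earlier in the same section, the investigator is to record "the severity grade (mild, moderate, severe, life-threatening, fatal") for each event, again with the last two as distinct categories.

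A neighbouring rule, under Relationship to Drug, is open-ended. For "Grade > 3 adverse reactions which are possibly (3), probably (4) or definitely (5) related to the drug", it says that "study medication should be discontinued as described above".

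Section XI asks the DSMB chair or designee to review each SAE report within 7 days of the investigator receiving the information, and "to confirm the grading of any toxicities and assure that they do not meet stopping criteria". Section XII's first criterion for an SAE is that the event "results in death".

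**The concern.** A termination rule that is triggered by one life-threatening reaction should plainly be triggered by one fatal reaction. IX.C names a single grade where a threshold was needed. Because the scale gives death its own grade, a related event whose only recorded grade is 5 does not match the words of the rule.

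This matters because the DSMB chair or designee is asked to compare graded events with these criteria. The population has a potentially fatal disease, so deaths are foreseeable and their relation to the drug may be disputed. Once a death has been judged related, the rule should not need interpretation as well.

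**Working it through.** The protocol gives no figure on this point to reproduce. The main check sets the severity scale in Section XII against the triggers in IX.C.

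| Grade | Meaning (Section XII) | Termination trigger in IX.C |
|---|---|---|
| 1 | Mild | None named |
| 2 | Moderate | None named |
| 3 | Severe | Two subjects, same related event, irreversible |
| 4 | Life-threatening | Any one related event |
| 5 | Fatal | None named |

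**Does another provision supply grade 5?** The discontinuation rule under Relationship to Drug covers everything above grade 3, so it includes grade 5. Its stated action, however, is on study medication, which has no practical meaning for a patient who has died. Its reference to something described above may point to IX.C but does not say so. The DSMB check in Section XI is made against the stopping criteria, which are those in IX.C. Neither provision clearly extends termination to grade 5.

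**Can an event be recorded only as grade 5?** Yes, if each event carries one recorded grade and the death was not preceded by a grade-4 entry. This is plausible. After discharge the family may give the infusion (Study Drug Administration), and anaphylactic reactions are among the listed undesirable effects (Section VI).

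**How often might this arise?** The documents give no rate, so the per-patient chance *p* of a related event recorded only as grade 5 is an assumption. With 25 patients (Sections IX.E and XIII), and treating patients as independent:

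P(at least one) = 1 − (1 − p)^25

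- p = 0.001: 1 − 0.999^25 = 0.0247, or 2.5%
- p = 0.005: 1 − 0.995^25 = 0.1178, or 11.8%
- p = 0.01: 1 − 0.99^25 = 0.2222, or 22.2%

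Section VII states that the available safety data show no life-threatening risks, so the low end is the better fit. The total of 25 is approximate: IX.E says so, and IX.I continues enrolment until 25 patients complete. The number treated could therefore be somewhat larger.

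**The case against.** The strongest reply is that a reaction which kills a patient has first put that patient at immediate risk of death, which is how Section XII defines grade 4. IX.C asks only whether a subject develops such an event, not whether 4 is its final or only grade. On that reading every related death is already covered. The reply is reasonable, and it succeeds outright for any fatal reaction first recorded as life-threatening. It does not settle a death that was only ever graded 5, because the scale gives death its own grade and the rule names a different one.

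Second, the discontinuation rule for reactions above grade 3 shows what the authors meant, and IX.C is the only earlier provision in the supplied text that stops anything by grade. This is good evidence of intent. It is not a statement that the study ends.

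Third, oversight would catch the case. A death is an SAE, it goes to the DSMB chair or designee, and nothing supplied limits the DSMB to the written triggers. This stands, and it is why the point carries little weight.

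Fourth, the assumed rates have no source in the documents, and they describe occurrence of the event rather than failure of the rule. That is also correct. The figures only give scale; the wording gap does not depend on them.

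**Conclusion.** The concern holds as a low-severity wording error in a safety rule. Read literally, IX.C leaves out related events whose sole recorded grade is 5. This rests on one recorded grade per event; where a grade-4 entry came first, there is no gap. The intended threshold is almost certainly grade 4 or higher. The finding is not evidence that the study would continue after a drug-related death.

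**What to change.** In IX.C, replace the reference to a related grade-4 adverse event with *a related grade-4 or grade-5 adverse event*. This brings the rule into line with the threshold above grade 3 that Section XII already uses for stopping study medication.

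Two further clarifications are optional: name the section meant by the back-reference in the discontinuation sentence, and add to IX.C a cross-reference to the relationship categories that Section XII treats as attributable.

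The cost is one phrase in a protocol amendment. Sample size, procedures, analysis and the existing meaning of related are unchanged.
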